Title: Botulinum toxin is a promising prophylactic therapy for minimizing post-excisional scarring: A Double Blinded, Randomized Controlled Trial

PI: [name]

PI: [name]

NCT02623829

Document Date: 7/9/2015

Botulinum toxin is a promising prophylactic therapy for minimizing post-excisional scarring:

A Double Blinded, Randomized Controlled Trial

Investigators:

[name]

[name]

Study Site:

Mount Sinai School of Medicine

Department of Dermatology

[name]

[name]

Financial Support:

Protocol Version: 1, 7/9/2015

Botulinum toxin is a promising prophylactic therapy for minimizing post-excisional scarring: A Double Blinded, Randomized Controlled Trial

Introduction and Rationale:

Dermatological surgeons wear many hats to care for subjects with skin cancer. While their role in cancerous tissue removal results in superior cure rates, there is also a need for skilled excisional repair and effective wound healing regimens so the subject can heal with the least amount of scarring necessary. As such, numerous techniques have been developed for reducing the morbidity associated with excessive scarring. Various flaps and grafts allow the surgeon to approximate skin texture, thickness and adnexa with respect to the residual surrounding tissue. However, for optimal cosmetic and functional outcome, specific suture techniques are often necessary to ensure close wound approximation while simultaneously minimizing static tension along the wound edge (1). In addition, there are post-operative techniques for wound care that range from special dressings during the various stages of healing to cosmetic procedures for scar modification. Unfortunately, once the operation is complete, there is little the surgeon can do to minimize adverse scar formation without impairing the healing process. To date, most surgical wounds are allowed to heal at least partially before scar revision or modulation is attempted.

Botulinum toxin presents a unique opportunity for surgeons to affect scar formation throughout the duration of the healing process. These effects are likely independent and adjunctive to any and all wound care techniques, and are primarily attributed to a reduction in dynamic tension on the wound edges (1). Most importantly, botulinum toxin's one time dosing requirements with respect to reduced scar formation precludes the variance inherent to standard wound care practices.

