Therefore, it has been proposed that for selected subjects, botulinum toxin may be a safe, effective and reliable means for improved post-excisional repair outcomes (2). Botulinum toxin has been investigated as an inhibitor of excessive, post-excisional scar formation in plastic surgery and Otorhinolaryngology literature (1-7). However, these promising studies have yet to combine objective assessment measures of human scar formation in a randomized controlled trial. In addition, there are currently no formal studies of botulinum toxin as a prophylactic against excess scarring in the dermatological literature. Fortunately, Botulinum toxin dosing in the forehead for the purposes of inhibiting excessive scar formation is comparable to the amount given for cosmetic purposes (5), which is commonplace in dermatology and well-studied (6-8).

Objective:

This study will attempt to assess the efficacy of Botulinum toxin as a prophylactic treatment in post-excisional repairs for the purpose of preventing excess scar formation. The end points will be the evaluation of each scar using the Manchester Scar Scale.

Description of Study:

We plan to enroll 40 subjects in this study who are scheduled for forehead excisions on the day of enrollment. Each qualifying subject will undergo post-excisional injections into the forehead and glabella. Twenty will receive 1ml of normal saline and 20 will receive a total of 50 units of botulinum toxin diluted in 1ml of normal saline. Both the subject and investigator will be blinded as to which site receives what. After these injections, the subject will proceed as per the normal standard of care for their post-operative care. Upon return for suture removal about a week later (as per normal standard of care), the subjects will all answer a brief questionnaire regarding any adverse events they may have had after the injections. They will then be scheduled for their last and only additional clinical visit for this study, at 24 weeks. Upon arrival for the final visit, the patient will again answer a brief questionnaire regarding any adverse events they may have had after the injections. After this, the assessment of response will be made utilizing the Manchester Scar Scale (MSS) both clinically and in a modified version via standardized photographs taken of the scar. The patient will then be discharged home, with their involvement in the study complete.

Method of injection:

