Prior to entering the study, the investigator or designated assistant will explain to each subject the nature of the study, its purpose, procedures, expected duration, alternative therapy available, and the benefits and risks involved in study participation. Subjects will be given the consent document, the opportunity to ask questions, and will be informed of their right to withdraw from the study at any time without prejudice. After this explanation and before any study-specific procedures have been performed, the subject will voluntarily sign and date and informed consent form, including photographic consent. Prior to participation in the study, the subject will receive a copy of the signed and dated written informed consent form.

Study Methodologies:

Visit 1 Screening/Baseline – Day 0 / Receive Injection

The following pre-study screening procedures should be completed prior to randomization and Treatment Initiation:

1. Obtain a signed and dated subject informed consent, including photographic authorization.
2. Review inclusion and exclusion criteria.
3. Collect demographic information including date of birth, sex, race, ethnicity, and underlying reason for excision.
4. If applicable, perform urine pregnancy testing.
5. After the excision is completed, the length of the defect will be recorded in addition to the number and type of sutures placed, final length of suture line and a photograph will be taken.
6. The subject will be randomly assigned to receive normal saline with or without botulinum toxin, prepared by outside party (recorded separately) and handed to dispensing physician and neither injector nor subject will know which.
7. Contents of syringe will be administered to forehead and glabella.
8. Schedule week 2 visit.

Visit 2 (Week 1 +/- 2 days, at suture removal as per normal standard of care)

The following procedures will be performed at this visit:

1. Review and record adverse events.
2. Sutures will be removed and unidentifiable photographs will be taken of the forehead.
3. Schedule final visit.

Visit 3 (Week 24 +/- 2 days)

The following procedures will be performed at this visit:

1. Review and record adverse events.
2. Subject will have their scar assessed clinically via the MSS and be photographed for later mMSS assessments.

Note: any treatment-related AEs or LSRs that are ongoing will be followed to resolution or to the investigator's satisfaction.

Primary Endpoints

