- 1) Difference between treated and control MSS scores for each scar at 6 months
- 2) Difference between treated and control average mMSS scores for each scar at 6 months
- 3) Difference between treated and control aggregate scores for each scar at 6 months

Lesion Assessment Guidelines:

All MSS and mMSS assessments will be performed in a standardized fashion. The mMSS assessments will be blinded and performed by board-certified dermatologists in the Department of Dermatology, Faculty Practice Associates, Icahn School of Medicine at Mount Sinai, New York City.

Botulinum and Saline Injection Guidelines:

50 units of Botulinum toxin will be injected into randomly assigned subjects. The same procedure will be carried out for administration of the saline.

Safety Evaluations:

Urine Pregnancy Tests

Females of childbearing potential will undergo a urine pregnancy test at Visit 1(Week 0). If the pregnancy test is positive at Visit 1 the subject will not be permitted to enroll in the study and will not receive study drug.

Adverse Reactions

At each visit, the subjects will be assessed for any of the following possible AEs:

- injection site pain
- ecchymosis
- eyelid/brow ptosis
- systemic effects, including nausea, fatigue, malaise, flu-like symptoms, headache, runny nose, diplopia, dysarthria, generalized muscle weakness, asthenia, blurry vision, ptosis, dysphagia, dystonia, urinary incontinence, breathing difficulties, rash.

Prior and Concomitant Medications:

At the initial visit, prior and concomitant medications and therapies will be reviewed as may pertain to exclusion from the study.

Restricted Medications/Treatments

Restricted medications and treatments prior to the study initiation are those that the investigator feels may indicate that the subject has an unstable medical condition, as described in the exclusionary criteria.

Subject Withdrawal or Discontinuation:

Subjects may choose to withdraw from the study or may be withdrawn by the investigator at any time without prejudice to their future medical care. Any subject who does not comply with the inclusion/exclusion criteria may be withdrawn from further participation in the study.

Discontinuation Procedures: Any subject who wishes to discontinue prematurely from the study should return to the study center for an End of Study Visit.

Adverse Event Definitions:

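### The prompted adverse-event list has no wound-healing item, although the study drug is injected into the forehead right after a forehead excision is closed

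*Combined protocol and SAP*

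**What the plan says.** The subsection on adverse reactions, under Safety Evaluations in the combined protocol and SAP, introduces its list with "At each visit, the subjects will be assessed for any of the following possible AEs". The entries are "injection site pain", ecchymosis, "eyelid/brow ptosis" and "systemic effects, including nausea, fatigue, malaise, flu-like symptoms, headache, runny nose, diplopia, dysarthria, generalized muscle weakness, asthenia, blurry vision, ptosis, dysphagia, dystonia, urinary incontinence", followed by breathing difficulties and rash. That makes 20 named terms, 3 local and 17 systemic, with ptosis appearing in both groups.

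Study Methodologies, Visit 1, sets the order on Day 0. Step 5 reads "After the excision is completed, the length of the defect will be recorded in addition to the number and type of sutures placed", and the final suture-line length is also recorded. Randomisation follows in step 6 and injection into the forehead and glabella in step 7. The inclusion criteria require the excision to be on the forehead.

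At Visit 2 (Week 1), step 1 is an open review of adverse events. Step 2 is "Sutures will be removed and unidentifiable photographs will be taken of the forehead". At Visit 3 (Week 24) the review again comes first and the clinical Manchester Scar Scale (MSS) second. Description of Study adds a short questionnaire at both visits "regarding any adverse events they may have had after the injections". Adverse Event Definitions covers any unfavourable medical event linked in time to protocol procedures and requires CTCAE recording. Data Analysis describes the scar scores and the Wilcoxon rank sum test and gives no adverse-event summary by arm.

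**The concern.** The list would suit a cosmetic injection study. Here the same injections are given into a region that has just been excised and sutured, and no listed term concerns that wound. Toxin effects are solicited by name, while wound complications depend on the subject or the staff raising them. Two sources collected with different intensity cannot be set side by side as a balanced safety description.

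The timing adds to this. At Visit 2 the adverse-event review is listed before the step in which staff handle the wound, and no healing assessment follows. The next scheduled question comes about 23 weeks later (24 − 1), so a wound problem treated elsewhere in between depends on unprompted recall.

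There is a secondary cost for the efficacy result. A wound complication may affect the contour, distortion and texture that the MSS scores. If it is not on record, an outlying score cannot be explained.

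**Working it through.** The plan states no figure on this point, so there is none to reproduce. The main check compares the sections.

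**1. List against procedure.** None of the 20 listed terms is infection, dehiscence, haematoma, necrosis or delayed healing. Ecchymosis and rash are the nearest, and neither describes the state of the wound. Visit 1, steps 5 to 7, places the injection after closure, on the same day and in the same region.

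**2. Other routes for wound events.** Four exist: the broad definition, CTCAE recording, the open review at Visits 2 and 3, and the any-event questionnaire. All four would admit a wound complication. None, as printed, asks about one.

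**3. What incomplete capture could cost.** Input from Description of Study: n = 20 per arm. Assumptions, because the documents give neither figure: true event rate p of 2%, 5% or 10%, and capture s of 100% or 50%. The chance of recording at least one event in an arm is 1 − (1 − p·s)^20.

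| Assumed rate p | Full capture | Half capture |
|---|---|---|
| 2% | 1 − 0.98^20 = 33% | 1 − 0.99^20 = 18% |
| 5% | 1 − 0.95^20 = 64% | 1 − 0.975^20 = 40% |
| 10% | 1 − 0.90^20 = 88% | 1 − 0.95^20 = 64% |

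**4. What full capture could still not show.** With zero events in 20, the one-sided 95% upper bound is 1 − 0.05^(1/20) = 13.9%. Power to separate the arms (two-sided 0.05, normal approximation, rough at these counts) is about 18% for 5% vs 15% and 42% for 5% vs 25%.

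**5. Effect on the scar comparison.** With 20 vs 20 and no ties, the rank-sum statistic U has null SD √(20 × 20 × 41 / 12) = 37.0. Moving one subject from a middle position to the worst shifts U by about 10, which is 10 / 37.0 = 0.27 SD. Two such subjects shift it by 20 / 37.0 = 0.54 SD.

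**The case against.** The strongest reply is that the plan already collects any adverse event. Subjects are actively questioned at both follow-up visits, the review is not confined to the list, and the definition covers events tied to protocol procedures. At Visit 2 staff take out the sutures and photograph the forehead, so an infection or open wound present then would probably be seen. The questionnaire's reference to events after the injections does not exclude wound events either: injection follows closure, so every postoperative complication comes after it. The questionnaire itself is not reproduced and might contain a wound question.

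All of this stands, and it limits the point to systematic capture. It does not remove it. A named list is the plan's own means of ensuring that particular effects are asked about, and it leaves out the wound.

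Three stronger readings are tempting, and the documents do not support them:

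- **That the plan itself names impaired healing as its safety concern.** The Introduction says only that once the operation is complete "there is little the surgeon can do to minimize adverse scar formation without impairing the healing process". That is background on surgical options. It is not a stated risk of the toxin, and the Objective is about efficacy.
- **That adverse-event collection is limited to the listed effects.** The four routes in the working show otherwise.
- **That the chance of a complication somewhere in the trial measures what would be missed.** At assumed rates of 2%, 5% and 10%, the chance of at least one among 40 is 55%, 87% and 99% (1 − 0.98^40, 1 − 0.95^40, 1 − 0.90^40). Those are chances that an event occurs and say nothing about whether it is recorded.

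**Conclusion.** The gap is real and modest. The prompted list has no wound-healing item in a trial that injects into the forehead straight after a forehead closure, so wound complications are likely to be captured less completely than toxin effects. How much less cannot be derived from the documents. Under the assumption of half capture, the chance of recording any event in an arm falls by about 15 to 24 percentage points across rates of 2% to 10% (33 − 18 = 15; 64 − 40 = 24; 88 − 64 = 24).

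The effect on the scar comparison is secondary. One displaced subject moves the rank-sum statistic by about a quarter of its null SD, and recording the complication would help explain the score without changing it.

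Prompted capture would give a complete and comparable description by arm. It would not show that healing is unaffected, since even zero events in 20 leaves a true rate of about 14% possible. The conclusion assumes that the questionnaire, which the documents do not show, has no wound question. If it has one, the remaining work is to align the printed list and the reporting with it.

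**What to change.** 1. Add wound infection, dehiscence, haematoma or bleeding, necrosis and delayed healing to the list under Safety Evaluations, each with a short definition.
2. At Visit 2, record each as present or absent in both arms, at or after suture removal.
3. At Visit 3, ask about wound problems or wound treatment since Visit 2, after the MSS has been scored, so that the answer cannot influence a partly subjective score. Description of Study and Visit 3 both put the adverse-event questions before scoring, so both need a matching edit.
4. In Data Analysis, state that these events will be tabulated by arm beside the toxin effects, as counts and percentages, without a claim of equivalence.

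The cost is about five tick-box items at existing visits and a few more recorded events in both arms. No visit is added. Problems arising between Weeks 1 and 24 would still rely on recall, but with a direct question.

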The mMSS will employ much of the MSS but will not include the assessment for texture since it will be applied to standardized photographs of each scar from each visit. Photographs will be taken at a distance of 10cm and cropped to include the scar and surrounding 1cm of normal skin. These photographs will then be assessed by a panel of Dermatologists at a later date. The scores will then be averaged to yield the mMSS average score for each scar at each visit.

Subject Selection:

Inclusion Criteria

1. English-speaking adults at least 18 years old.
2. Subjects must be scheduled for an excision of forehead skin due to any etiology, with a simple linear closure planned as the most likely surgical repair.
3. Subjects must be able to read, sign, and understand the informed consent.
4. Subject is willing and able to participate in the study as an outpatient, making several visits to the study center during the treatment and follow-up periods and to comply with all study requirements including concomitant medication and other treatment restrictions.
5. If subject is a female of childbearing potential she must have a negative urine pregnancy test result prior to study treatment initiation and must agree to use an approved method of birth control while enrolled in the study.

Exclusion Criteria

1. Subjects with an unstable medical condition as deemed by the clinical investigator, including review of the subject's prior and current medications.
2. Subjects with Myasthenia gravis, Lambert-Eaton Syndrome or other neuromuscular disorder.
3. Subjects taking medications that may alter the function of neuromuscular junctions (i.e. aminoglycoside antibiotics)
4. Women who are pregnant, lactating, or planning to become pregnant during the study period.
5. Subjects who have a history of keloids.
6. Known allergy to botulinum toxin.
7. Subjects who are not able to be closed with a simple linear technique

Informed Consent:

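### Must the plan change because recent forehead botulinum toxin is not named at entry and no listed visit step records toxin or scar treatment up to week 24?

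*Combined protocol and SAP*

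**What the plan says.** **Entry.** The only exclusion that names the product is Criterion 6: "Known allergy to botulinum toxin". Criterion 3 removes "Subjects taking medications that may alter the function of neuromuscular junctions (i.e. aminoglycoside antibiotics", with no look-back period. The Prior and Concomitant Medications section adds: "At the initial visit, prior and concomitant medications and therapies will be reviewed as may pertain to exclusion from the study". The next section, Restricted Medications/Treatments, covers only treatments that suggest unstable health: "Restricted medications and treatments prior to the study initiation are those that the investigator feels may indicate that the subject has an unstable medical condition". Inclusion Criterion 4 asks subjects to "comply with all study requirements including concomitant medication and other treatment restrictions", but no on-study restriction is set out anywhere.

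**Recording.** The history item at Visit 1 is "Collect demographic information including date of birth, sex, race, ethnicity, and underlying reason for excision"; the other steps are consent, eligibility review, pregnancy test, wound and suture details with a photograph, randomisation, injection and scheduling. Visit 2 lists adverse events, suture removal with photographs, and scheduling. Visit 3 lists adverse events and then "Subject will have their scar assessed clinically via the MSS and be photographed for later mMSS assessments". The Description of Study mentions a questionnaire at the last visit, but its subject is side effects: "the patient will again answer a brief questionnaire regarding any adverse events they may have had after the injections". Post-operative care is left to normal practice in both arms.

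**Analysis.** The Data Analysis section plans an unadjusted Wilcoxon rank-sum comparison of 20 against 20.

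**The concern.** The exposure that might go unseen is the study drug itself, in the region where the study injects it. The Introduction credits the benefit to lower dynamic tension on the wound edges and describes cosmetic forehead dosing as common in dermatology. A saline subject with recent cosmetic toxin may already have part of that benefit, and a toxin subject with the same history may have less to gain. Either would shrink the difference between arms.

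After Day 0 there is no study contact between week 1 and week 24, a gap of 23 weeks. The Introduction says scar revision is usually attempted only after partial healing, so it could fall in that gap. If such treatment were used more in one arm, the week-24 difference could move either way. With 20 per arm and no recorded exposure, nobody could check afterwards.

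**Working it through.** **Step 1: the entry text.** Criterion 3 turns on drugs that alter the neuromuscular junction, which botulinum toxin does. Against that, it speaks of subjects who are taking a drug, and it names only aminoglycosides. But the entry review covers prior as well as current therapies, and Visit 1 includes a check of all criteria. An investigator can therefore reach recent toxin under the text as it stands. What is missing is the name and a time window. The restrictions that Inclusion Criterion 4 mentions without listing are a loose end in the wording.

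**Step 2: the recording text.** The visit lists are not complete inventories. The medication review takes place at the initial visit but is not itemised under Visit 1, and the questionnaires are not itemised under Visits 2 and 3. Absence from a list is thus weak evidence of absence from the form. Adverse-event review covers part of the gap: the Adverse Event Definitions exclude surgery itself but include a condition, arising during the study, that requires it. A scar that needed surgical revision would be reported as a condition. Elective cosmetic toxin would not.

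**Step 3: earlier toxin, illustrated.** The plan states no power, alpha, SD or effect, so there is no figure to reproduce. From the plan: 20 per arm and the Wilcoxon test. Assumed: effect 0.9 SD, normal scores, two-sided 0.05 (exact critical value U ≤ 127), 200,000 simulated trials per setting. A share p of both arms has had earlier toxin. If exposed subjects show no treatment difference, the mean contrast is 0.9 × (1 − p); if they keep half, it is 0.9 × (1 − p/2).

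| p | Contrast, none kept | Power | Contrast, half kept | Power |
|---|---|---|---|---|
| 0% | 0.900 | 76.8% | 0.900 | 77.0% |
| 2% | 0.882 | 75.0% | 0.891 | 76.0% |
| 5% | 0.855 | 71.9% | 0.878 | 74.6% |
| 10% | 0.810 | 66.8% | 0.855 | 72.3% |
| 20% | 0.720 | 55.6% | 0.810 | 67.2% |

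With no study-drug effect and earlier toxin worth 0.9 SD in both arms, the rejection rate is 4.8% at p = 10% and 5.0% at p = 20%.

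The chance that none of the 40 subjects is exposed is (1 − p)^40: 45% at 2%, 13% at 5%, 1.5% at 10%. The chance that the arms differ by three or more exposed subjects (two independent binomials of size 20) is 1%, 7%, 18% and 32% at 2%, 5%, 10% and 20%.

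**Step 4: later treatment, illustrated.** Assume it improves a scar by 0.45 SD and is used by shares t (toxin) and s (saline). The contrast is 0.9 + 0.45 × (t − s).

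- 5% of saline only: 0.9 − 0.0225 = 0.8775, power 75%.
- 5% of toxin only: 0.9225, power 79%.
- 20% of saline only: 0.81, power 67%.
- 20% of toxin only: 0.99, power 83%.
- 10% of each arm: 0.90, power 76%.

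**Step 5: what the extra data would buy.** At p = 10%, leaving out subjects exposed before randomisation gives 20 × 0.90 = 18 per arm and about 72% power, against 67% with everyone kept. That is roughly 5 points, from an imprecise secondary analysis. The primary analysis would keep all randomised subjects in any case.

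**The case for a change.** The best case for a change is that it is cheap and the information is hard to recover later. One eligibility line, one form item per visit and one table by arm would settle whether exposure was rare, and even a row of zeros would help a reader. Two investigators could decide differently about recent toxin under Criterion 3. At 20% exposure the power loss could reach 21 points, and the chance of a noticeable imbalance is about one in three.

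Much of this stands as a matter of clarity. Toxin is not named, no look-back is given, Inclusion Criterion 4 refers to restrictions that are listed nowhere, and elective toxin during follow-up would not appear as an adverse event.

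What does not stand is the step to a defect in the plan. The large losses need 10% to 20% of subjects to pass the entry review despite recent toxin. The upper figures also treat earlier toxin of any age or dose as equal to a fresh study injection. Common use in dermatology is not a prevalence among people having a forehead excision. As for later treatment, usual care runs in both arms, so its use can be a fair part of what the randomised comparison measures.

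**Conclusion.** No change to the plan is called for. The gaps are real but are missing detail that investigators and form designers can fill sensibly: the eligibility text can be read to reach recent toxin, the unlisted restrictions are loose wording, and the form may already ask for treatments. The randomised comparison stays valid and the planned test would not alter. Extra items would feed a descriptive table only.

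At 2% to 5% earlier exposure the illustrated cost is 1 to 5 points of power. Later treatment used by 5% of one arm moves the contrast by about 0.02 SD. These sizes rest on an assumed 0.9 SD effect, an assumed 0.45 SD for later treatment and assumed exposure shares, none of them in the documents; the true size is unknown. The absence of false positives applies to toxin given before randomisation. Treatment after Day 0 can shift the difference in either direction, but then it belongs to the comparison of each injection followed by usual care. Naming toxin, tidying Inclusion Criterion 4 and adding a treatment item to the form would be a reasonable optional clarification, with any rule left to the sponsor.
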